The main goal of this project is to measure kidney filtration function at day 14 of the ICU stay or the day of discharge from the ICU (whichever occurs first), in order to determine the presence and *magnitude of persistent kidney dysfunction after sepsis episode and to longitudinally assess* further decline of kidney function at one year follow-up. In our initial IRB protocol we have proposed to use iohexol clearance as a gold standard that provides most accurate determination of glomerular filtration rate (GFR). Unfortunately we have not been able to recruit patients into the study as designed due to the complexity of this procedure and need for a dedicated IV line. Since one of the main goals of the overall project is to determine the decline in glomerular filtration rate from the sepsis episode to the one year follow up, we have considered different approaches, in order to be able to obtain this valuable data.

We propose to offer patients four complementary ways for GFR assessment, both at approximately day 14 or approximately at the day of discharge from the ICU and at the one year follow up :

1. Determine clearance of iohexol from blood after iohexol injection and/or
2. Determine appearance of iohexol in urine after iohexol injection (this would be the same injection as in one, and would not require two injections) and/or
3. A timed urine collection to determine clearance of urea and creatinine and/or
4. Estimated GFR using calculations with serum creatinine, if performed clinically if not we will draw it specifically for the study, and cystatin C, performed specifically for the study. Currently any patient that is enrolled in this protocol will already be a part of IRB201400611 and will already be getting serum creatinine, cystatin C and a urine microalbumin/creatinine ratio drawn at the one year appointment.

This approach will allow us to maximize recruitment of patients into the study by providing flexibility, but it also provides an important opportunity to validate the different measurements against the gold standard, iohexol clearance. For all patients we will also obtain a urine microalbumin/creatinine ratio as another important determinant of structural kidney damage.

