We also propose to include stage 3 AKI patients on renal replacement therapy, who were previously excluded. Some of these patients do recover after initial episode and will present at one year follow up. It will be very valuable for us to understand factors leading to recovery. For these patients we will use only methods 2 and/or 3 for estimation of GFR, both of which are safe. Even patients who are dialysis dependent have some level of residual renal function and even if they make even a minimal amount of urine this may be an important determinant of renal recovery.

The assessments will be performed approximately 72 hours within day 14 or the anticipated discharge from the ICU and at 1 year follow-up.

Given the loss of muscle mass in chronic critical illness, we will measure, rather than estimate glomerular filtration rate, to determine whether unrecognized kidney dysfunction in late sepsis drives inflammation and catabolism, contributing to poor long term survival and development of chronic kidney disease. For the assessment of glomerular filtration rate, the most frequently used clinical test is serum creatinine, despite the fact that its accuracy depends on a constant muscle mass, which is almost never the case with patients with chronic critical illness. We have previously demonstrated that sepsis and chronic critical illness are associated with a rapid and significant loss of lean muscle mass over time. Even a small fall of 25% in muscle mass should lead to a fall in serum creatinine of 25%. Thus in a chronic critical illness patient hospitalized for 4 weeks, the persistent increase in serum creatinine from a baseline of 1.0 mg/dl to 1.5 mg/dl implicates a significant drop in glomerular filtration rate; assuming a 50% reduction in muscle mass, in this individual a serum creatinine of 1.5 would reflect glomerular filtration rate of ~ 37 mL/min/1.73 m², consistent with stage 3 chronic kidney disease. To determine whether unrecognized decline in kidney function contributes to persistent inflammation, decreased protein intake, and muscle wasting in chronic critical illness it is necessary to measure glomerular filtration rate rather than estimate it.

5. Specific Aims:

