The goal of this study is to determine to what extent persistent kidney dysfunction contributes to inflammation, catabolism and long-term mortality in chronic critical illness. We will test the working hypothesis that persistent kidney damage in chronic critical illness contributes to decreased survival through persistent inflammation, immunosuppression and catabolism.

6. Research Plan:

Study overview and design

This is a prospective, longitudinal, case-control study involving a subset of the initial cohort of 400 sepsis subjects enrolled in IRB STUDY #2014-611 who agree to measurement of glomerular filtration rate using iohexol clearance and the amended measurements listed above. Assuming a minimum 70% recruitment rate, we expect to enroll minimum of 230 patients and maximum of 400.

Identifying patients and consent

All sepsis patients who consent to enroll in the IRB Project #2014-611 and meet inclusion/exclusion criteria will be asked for enrollment in this study after they are consented for the IRB Project #2014-611. The informed consent will be obtained by the same research staff

within the Human Subject Core of the University of Florida P50 Center. Since many sepsis patients in the surgery and trauma ICUs may have altered mental status or pharmacologic sedation, but would be regarded as prospective research subjects a legal authorized relative (LAR) or next of kin would be approached for informed consent. The research nurse will monitor the patient's progress and once they regain capacity, the patient will be reconsented.

Inclusion Criteria

- a) Presence in the surgery or trauma ICU where clinical care can be managed by surgical critical care guided by standard operating procedures.
- b) Age of ≥ 18 years
- c) First entrance into our sepsis protocol at Shands/UF on index admission.
- d) Ability to obtain informed consent.

Exclusion criteria

Expected lifespan of the patient is less than 3 months due to severe pre-existing comorbidities (ex. recurrent, advanced or metastatic cancer).

- b) Severe traumatic brain injury (evidence of neurologic injury on CT scan and a GCS <8)
- c) refractory shock (i.e., patients who die within 12 hours)
- d) uncontrollable source of sepsis (e.g., irreversible disease state such as unresectable dead bowel)
- e) Patient or patient's family are not committed to aggressive management of the patient's condition.
- f) severe CHF (NY Heart Association Class IV)

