The patients will be asked to return for a one year follow up appointment that will occur with the one year appointment from IRB protocol #2014-611 at the Institute on Aging. The patients will receive a \$25 compensation for the inpatient portion of the study and a \$75 compensation for their time when they return for the one year follow up visit. At one year follow-up all measurements for iohexol clearance, will be performed in CTSI. Timed urine collection at one year follow up will be performed at home and all necessary supplies will be mailed to patient. If the patient did not do a timed collection, but is still willing to perform timed urine at the time of the CTSI visit, we will time the urine collection during their CTSI visit. For patients who opt only for serum creatinine/cystatin C measurement and spot urine microalbumin/creatinine ratio, urine and blood will be collected in the CTSI as a part of the IRB protocol #2014-611.

Primary Outcomes

We will compare:

Protocol

IRB version 03.09.04

PI version 9/10/2015

- a) The decline in glomerular filtration rate at 1-year follow-up between chronic critical illness and control groups.
- b) Correlation between iohexol glomerular filtration rate and estimated glomerular filtration rate using previously validated equation applied to serum creatinine.
- c) Development of de novo albuminuria or progression of existing albuminuria.

Data Collection and Analyses

All relevant clinical and laboratory variables for this cohort will be uploaded directly into the REDCap case report form (CRF) from the EPIC EMR for the main STUDY IRB#2014-611.

Sample size and feasibility. Assuming that chronic critical illness patients have at least a two-fold decline in glomerular filtration rate as compared to the average glomerular filtration rate decline of 6 ± 16 ml/yr, the sample size of 150 chronic critical illness and 80 control subjects will offer 80% power at a two-sided significance of $P=0.05$.

Data analyses and interpretation. The parametric and non-parametric tests for difference between two independent samples will be used to compare decline in glomerular filtration rate between chronic critical illness. Using the Cox survival model we will test the multivariate relationship between glomerular filtration rate at day 14 and survival status at year 1.

Protection of Privacy and Confidentiality

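### The stated 80% power is about 77% at 150 + 80 even with complete data, and it makes no allowance for patients without a measured GFR at both visits

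*Combined protocol and SAP*

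**What the plan says.** The sample size paragraph in section 6 assumes that chronic critical illness (CCI) patients lose GFR at no less than twice an "average glomerular filtration rate decline of 6 ± 16 ml/yr". From this it concludes that "the sample size of 150 chronic critical illness and 80 control subjects will offer 80% power at a two-sided significance of" 0.05. The total of 230 is the lower end of the enrolment range of 230 to 400 in the study overview, which also assumes recruitment of at least 70% from a parent cohort of 400.

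The plan says several things about how GFR is obtained:

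- The Background (section 4) argues from muscle loss in CCI that "it is necessary to measure glomerular filtration rate rather than estimate it".
- The Background also reports on the iohexol-only design: "Unfortunately we have not been able to recruit patients into the study as designed due to the complexity of this procedure". It then offers four methods joined by and/or: iohexol in blood, iohexol in urine, timed urine clearance, and estimated GFR from creatinine and cystatin C.
- The one-year visit text makes provision "For patients who opt only for serum creatinine/cystatin C measurement and spot urine microalbumin/creatinine ratio".
- The study overview still describes the enrolled subset as those "who agree to measurement of glomerular filtration rate using iohexol clearance and the amended measurements listed above".
- Patients on renal replacement therapy (RRT) are limited to methods 2 and/or 3, and patients with a known contrast allergy do not have iohexol clearance.

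Primary outcome (a) is the one-year decline in GFR, CCI against control. It names no GFR method.

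**The concern.** There are two separate problems with the power statement.

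First, the stated inputs do not give 80% at the stated group sizes, even if every patient contributes a value at both visits.

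Second, the statement counts 230 contributing patients, which is the whole of the minimum enrolment. The amended design no longer ensures that each enrolled patient has a measured GFR. A patient who chooses only creatinine and cystatin C has no measured value by any method, and the decline needs a value at both visits. This would arise even if nobody died or missed the one-year visit.

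What is at stake is interpretation. If the measured-GFR comparison shows no clear difference, a reader who relies on the plan will take that as the result of a study with 80% power. The number of patients behind the comparison may not support that figure.

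**Working it through.** **Inputs, all from the sample size paragraph unless noted**

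- Control decline 6 ml/yr and CCI decline 2 × 6 = 12 ml/yr, so the difference is 6.
- Spread 16 ml/yr. The plan does not label it; it is read here as an SD common to both groups.
- Two-sided alpha 0.05.
- 150 CCI and 80 control, a ratio of 1.875.
- Enrolment of 230 to 400 (study overview); 70% × 400 = 280.

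**Reproducing the stated 80%**

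Standardised difference: 6/16 = 0.375.

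Standard error: 16 × √(1/150 + 1/80) = 2.215.

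Noncentrality: 6/2.215 = 2.709.

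Critical t on 228 degrees of freedom: 1.970.

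Power from the noncentral t distribution is **77.0%**. The normal approximation, Φ(2.709 − 1.960), gives 77.3%. The stated 80% is not reproduced.

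The number needed for 80% at this ratio, by the normal formula for the control group, is (1.960 + 0.842)² × 16² × (1 + 1/1.875)/6² = 85.6, rounded up to 86. That goes with about 162 CCI patients, or **about 248** in all; solving with the t distribution also gives 248. For comparison, 230 split equally (115 + 115) gives 80.8% by the t-test. The stated figure would therefore fit an equal split, but the plan does not say that it was derived that way.

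**Effect of incomplete measured pairs**

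The documents do not give the share with a measured GFR at both visits. It is an assumption here, applied equally to both groups with the 150:80 ratio kept. Group sizes are 150/230 and 80/230 of (enrolled × share). Power by t-test:

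| Share with a measured pair | 230 enrolled | 280 enrolled | 400 enrolled |
|---|---|---|---|
| 100% | 77.0% | 84.6% | 94.6% |
| 90% | 72.5% | 80.6% | 92.2% |
| 80% | 67.4% | 75.9% | 89.0% |
| 70% | 61.5% | 70.1% | 84.6% |
| 60% | 54.9% | 63.4% | 78.7% |
| 50% | 47.6% | 55.5% | 71.0% |

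In the 230 column, 80% means 120 + 64 patients, 70% means 105 + 56, and 50% means 75 + 40.

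The share needed for 80% power is 248/280 = 89% at 280 enrolled and 248/400 = 62% at 400. At 230 it cannot be reached.

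**Separating the two effects**

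At 230 enrolled, 3.0 of the points below 80% are lost before anyone opts out. Going from a full share to 90% costs a further 77.0 − 72.5 = 4.5 points.

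**The case against.** The strongest reply is that 230 is only the minimum. Enrolment may reach 400, and then 230/400 = 57.5% uptake still leaves 230 measured pairs. This stands. A reader might infer that the measured comparison must fall well short of 80%, or run at about half of it. The documents support neither. Half of 80% would need roughly 40% uptake at the minimum enrolment (39.6% power), and the plan gives no uptake figure.

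A second reply concerns who is lost. A reader might infer that RRT patients, and all who decline iohexol, drop out of any measured comparison. They do not. In the Background's four-item list, methods 2 and 3 are urine iohexol and timed urine clearance, so RRT patients are kept only from the blood method. A patient who declines iohexol can still do a timed collection. This also stands. It leaves untouched the patients who choose only creatinine and cystatin C. The procedure descriptions later in section 6 number the methods differently (2 is timed urine and 3 is estimated GFR), so the two lists need reconciling.

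A third reply is that outcome (a) does not require measured GFR, so pooling all methods need not reduce the count. That is correct as a reading of the outcome. But the Background's case for measuring rests on serum creatinine failing under muscle loss, so pooling would bring in values that the plan itself calls unreliable for CCI. The argument does not cover cystatin C, and the plan does not say whether estimated values count. That gap is a reason to name the method.

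Lastly, the study overview can be read as saying that the 230 all agree to iohexol. The opt-out in the one-year visit text contradicts that reading.

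**Conclusion.** The point holds in two parts. The arithmetic part needs no assumption about uptake: at 150 + 80 the stated inputs give 77.0%, not 80%, if 16 is a common SD and the difference is 6 ml/yr. The shortfall is small, but it leaves no slack at the stated size.

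The second part is that the power statement was not reconciled with optional measurement. At the minimum enrolment, any opt-out to estimated GFR lowers the power of a measured comparison further, to 72.5% at a 90% share and 47.6% at 50%. Larger enrolment could offset this wholly or partly, so the final power cannot be settled from the documents. These figures assume equal uptake in both groups and no loss to death or non-return. The plan should be changed, and the change is one of wording.

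**What to change.** 1. In primary outcome (a), name the GFR methods that count as measured.
2. In the sample size paragraph, restate the power as about 77% for 150 + 80 with complete measured pairs. Add the power for the number expected to have a measured pair, using the uptake seen since the amendment. If that is not available, give a range labelled as an assumption, together with the enrolment it refers to.
3. In the study overview, reword the description of the enrolled subset so that the 230 are not presented as all agreeing to iohexol.
4. Report the measured-GFR comparison with its own number per group and 95% CI. Do not cite 80% power for it unless the number achieved supports that figure.

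This needs no extra patients or procedures. The cost is a less favourable stated power.

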Protocol

Project Title: Persistent Inflammation, Immunosuppression and Catabolism Syndrome (PICS): A New Horizon for Surgical Critical Care

Subtitle. Kidney Response to Sepsis Affects Angiogenic Balance and Likelihood of CCI and PICS

2. Investigator(s):

[name]., Ph.D.

[name].

[name].

[name].

3. Abstract:

Approximately a third of those patients who survive an early sepsis episode linger in the intensive care unit with manageable organ dysfunction without meeting criteria for established late multi-organ failure. Their clinical course is characterized by ongoing protein catabolism with poor nutritional status, poor wound healing, and recurrent infections. These patients are commonly discharged to long-term, acute care facilities, but due to excessive loss of lean body mass and their immunosuppressed state, they often develop secondary nosocomial infections and are rarely able to return to a fully functional state. The overall hypothesis of this program grant is that persistent inflammation, immunosuppression and catabolism (PICS) are the hallmark of pathophysiologic processes leading to a decrease in long-term survival and functional capacity in patients with chronic critical illness. This study investigates the mechanism by which kidney dysfunction perpetuates inflammation, immunosuppression, and catabolism in chronic critical illness. In a prospective, longitudinal, case-control study of sepsis patients with one year follow-up using iohexol clearance we will measure glomerular filtration rate in patients with chronic critical illness and controls (sepsis patients discharged from ICU before day 14) to determine to what extent degree of kidney dysfunction contributes to decreased survival and increase in chronic kidney disease at year one after sepsis onset.

4. Background:

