Approximately a third of those patients who survive an early sepsis episode linger in the intensive care unit with manageable organ dysfunction without meeting criteria for established late multi-organ failure. Their clinical course is characterized by ongoing protein catabolism with poor nutritional status, poor wound healing, and recurrent infections. These patients are commonly discharged to long-term, acute care facilities, but due to excessive loss of lean body mass and their immunosuppressed state, they often develop secondary nosocomial infections and are rarely able to return to a fully functional state. The overall hypothesis of this program grant is that persistent inflammation, immunosuppression and catabolism are the hallmark of pathophysiologic processes leading to a decrease in long-term survival and functional capacity in patients with chronic critical illness. This study investigates the mechanism by which kidney dysfunction perpetuates inflammation, immunosuppression, and catabolism in chronic critical illness. We will test the working hypothesis that persistent kidney dysfunction in sepsis associated chronic critical illness contributes to decreased survival through the development of persistent inflammation, immunosuppression and catabolism. In chronic critical illness, the persistence of inflammatory state may lead to capillary rarefaction in the kidney causing accelerated chronic kidney disease. Progression of chronic kidney disease during chronic critical illness can drive persistent inflammation, immunosuppression and catabolism. Indeed, many of the features of chronic critical illness are consistent with the protein-energy malnutrition and muscle wasting associated with chronic kidney disease. Thus the kidney can play a contributory role in chronic critical illness and PICS, respectively.

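### Primary outcome (a), one-year GFR decline in chronic critical illness versus control, has only unadjusted two-sample tests, though the groups are not randomised and only returning survivors are measured

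*Combined protocol and SAP*

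**What the plan says.** Under Primary Outcomes, item (a) is the decline in GFR at one year, compared between CCI and control groups. The abstract defines the comparison group as "controls (sepsis patients discharged from ICU before day 14", so ICU course decides group membership.

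The section on determination of GFR takes the change from the GFR at discharge to the GFR at one year. The Background section sets the index measurement at day 14 or at ICU discharge, whichever comes first. For the second measurement, "The patients will be asked to return for a one year follow up appointment".

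Under Data analyses and interpretation, the only method given for (a) is: "The parametric and non-parametric tests for difference between two independent samples will be used to compare decline in glomerular filtration rate". The sentence then breaks off after naming the CCI group; the missing words are presumably the control group.

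Two other places could be mistaken for adjustment of (a):
- "Using the Cox survival model we will test the multivariate relationship between glomerular filtration rate at day 14 and survival status at year 1". The outcome here is survival.
- An adjustment for loss of muscle mass, which belongs to the comparison of iohexol GFR with estimated GFR, outcome (b).

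On data, "All relevant clinical and laboratory variables for this cohort will be uploaded directly into the REDCap case report form" from the electronic record. On size, "the sample size of 150 chronic critical illness and 80 control subjects will offer 80% power".

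**The concern.** An unadjusted two-sample test answers the question in (a) only if the groups would have declined alike apart from CCI, and if those measured at one year represent those enrolled. The design secures neither.

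Patients who stay in ICU to day 14 may differ from those who leave earlier in age, prior kidney function and other factors that influence later decline. Their index GFR is also taken at a different point after sepsis onset. The plan's working hypothesis is that kidney damage in CCI lowers survival, so who is alive to be measured may depend on kidney function. Of the newly admitted patients on renal replacement therapy it says: "Some of these patients do recover after initial episode and will present at one year follow up".

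The Background section also suggests that in CCI "the persistence of inflammatory state may lead to capillary rarefaction in the kidney causing accelerated chronic kidney disease", so a difference on (a) may well be read as an effect of CCI. A positive or a null result could instead reflect who was in each group and who came back. A larger sample does not cure this: the bias stays while the standard error shrinks.

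**Working it through.** **Inputs from the documents.** SD of decline 16 ml/yr; average decline 6 ml/yr, doubled in CCI, so a difference of 6; 150 CCI and 80 controls; two-sided 5%; maximum enrolment 400 (about 261/139 at the same ratio). **Assumed**, because the documents give no figures: covariate correlations, imbalances, loss rates and odds ratios.

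**1. The plan's own figure.** SE = 16 × √(1/150 + 1/80) = 2.215. Noncentrality = 6/2.215 = 2.71. Power is 77.0% (noncentral t) or 77.3% (normal), against the stated 80%. That shortfall is a separate matter; 77% is the reference below.

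**2. Confounding with no true difference.** If a covariate has correlation r with decline and differs by d SD between groups, the spurious difference is r × d × 16.

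| r | d | Spurious difference (ml/yr) | Rejection at 150/80 | Rejection at 261/139 |
|---|---|---|---|---|
| 0.2 | 0.3 | 0.96 | 7.2% | 8.8% |
| 0.3 | 0.5 | 2.4 | 19.0% | 29.7% |
| 0.5 | 0.8 | 6.4 | 82.0% | 96.7% |

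The nominal rate is 5%. The direction follows the sign of r × d, which is unknown.

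**3. Selective loss with a true difference of 6.** Let z be standardised decline within group and logit(loss) = a + log(OR) × z, with a chosen to give the loss rate. Observed difference = 6 + 16 × (mean z kept in CCI − mean z kept in control). An OR above 1 means faster decliners are lost more often.

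| Loss CCI/control | OR CCI, control | Mean z kept CCI, control | Observed difference |
|---|---|---|---|
| 30/10% | 3, 3 | −0.270, −0.098 | 3.2 |
| 30/10% | 0.5, 0.5 | 0.190, 0.066 | 8.0 |
| 30/30% | 2, 2 | −0.190, −0.190 | 6.0 |
| 30/30% | 2, 1 | −0.190, 0 | 3.0 |
| 30/30% | 0.5, 1 | 0.190, 0 | 9.0 |
| 30/30% | 2, 0.5 | −0.190, 0.190 | −0.1 |
| 15/15% | 2, 1 | −0.098, 0 | 4.4 |

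Equal retention therefore protects the contrast only if the reasons for loss act alike in both groups. Loss unrelated to decline costs power only: 30/10% leaves 105/72 and power of 68%.

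**4. Cost of adjustment.** With p = 150/230, the variance of the adjusted difference relative to the unadjusted is (1 − r²)(1 + p(1 − p)d²), and p(1 − p) = 0.2268.

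| r | d | Variance factor | Power |
|---|---|---|---|
| 0 | 0.25 | 1.014 | 76% |
| 0 | 0.75 | 1.128 | 72% |
| 0.2 | 0.3 | 0.980 | 78% |
| 0.2 | 0.5 | 1.014 | 76% |
| 0.2 | 0.8 | 1.099 | 73% |
| 0.3 | 0.8 | 1.042 | 75% |
| 0.5 | 0.3 | 0.765 | 87% |
| 0.5 | 0.8 | 0.859 | 83% |

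A predictive covariate does not always reduce the variance: a weak predictor with a large imbalance raises it.

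**The case against.** **Change scores already deal with baseline differences.** In part. A constant difference in GFR level cancels, so a reader should not infer that a lower pre-sepsis GFR in one group by itself biases (a). Differences in rate of decline, regression to the mean and index timing do not cancel.

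**The plan works to retain patients.** It does: a visit shared with the parent study, payment, mailed urine kits with a fallback at the visit, and a blood and spot-urine option. These may well reduce non-return. They do nothing about death, and they are not an analysis.

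**The adjustment may be elsewhere.** The parent protocol is not among the documents, and the key sentence is visibly incomplete. But this plan refers to the parent study for data capture and visits, not for the analysis of (a), and the missing words look like no more than the comparator.

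**The figures show only that bias is possible.** True. The assumed ranges are wide and do not tell us which case applies. They support prespecifying an adjusted analysis, not a forecast of the result.

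**Stronger readings the documents do not support.**
- That the bias has a known direction: nothing in the plan fixes it.
- That the plan asserts (a) as a causal effect of CCI: it says only that the groups will be compared, and its working hypothesis makes kidney damage the exposure.
- That patients who do not recover will not return: it says only that some who recover will.
- That attrition was certainly ignored: enrolment of at least 230 equals 150 + 80, which suggests no allowance, but the same sentence assumes 70% recruitment from 400, which is 280. The passage is inconsistent and does not settle the matter.

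**Conclusion.** The point stands as one about the choice of analysis. As written, (a) is an unadjusted contrast, among survivors who return, between groups formed by ICU course, and nothing else in the documents covers that gap. The omission is certain; its numerical effect is not. At 150/80 a null difference would be rejected in about 7% to 82% of studies if an unadjusted covariate correlates 0.2 to 0.5 with decline and is imbalanced by 0.3 to 0.8 SD. Under the assumed loss patterns shown, a true 6 could appear as anything from about −0.1 to 9.0. These are illustrations resting on assumed inputs, not bounds and not predictions. The change should be made; confidence in its practical importance is medium.

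**What to change.** 1. Make the primary analysis of (a) a linear regression of decline on group, adjusted for prespecified pre-sepsis covariates from the planned record and REDCap feed: age at minimum, and pre-admission creatinine where available (its availability is an assumption). Report the planned unadjusted tests beside it.
2. Describe (a) as an adjusted association among one-year survivors with both GFRs. Report deaths, surviving non-returners and dialysis dependence at one year by group. State that index timing differs by group by construction and cannot be fully separated from CCI.
3. Add one sensitivity analysis for surviving non-returners: multiple imputation of decline, with the imputed values shifted separately by group, reporting where the conclusion changes. Shifts up to one SD (16) are reasonable: in the 30% loss, OR 2 case, kept patients average 0.190 × 16 = 3.04 below their group mean, so lost patients average 3.04/0.30 = 10.1 above the kept. The shifts must be group-specific, because a common OR at equal loss leaves the contrast at 6.0 while unequal ORs do not.

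**Cost.** Modest extra analysis work, with no change to study procedures. Against 77% unadjusted at 150/80, power is about 72% to 76% if the covariate is imbalanced (0.25 to 0.75 SD) but not predictive, and about 73% to 87% if it is predictive (r 0.2 to 0.5, d 0.3 to 0.8). Adjustment removes measured confounding only; unmeasured confounding and the index-timing difference remain.
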